5. STUDY TREATMENTS

5.1. Investigational Product

Mepolizumab (SB-240563) is a fully humanised IgG antibody (IgG1, kappa) with human heavy and light chain frameworks. Mepolizumab will be provided as a lyophilised cake in sterile vials for individual use. The vial will be reconstituted with Sterile Water for Injection, just prior to use. Further details of dose preparation and administration can be found in the Clinical Investigator's Brochure (CIB), and the Study Procedures Manual (SPM).

The contents of the label will be in accordance with all applicable regulatory requirements.

Under normal conditions of handling and administration, investigational product is not expected to pose significant safety risks to site staff. Take adequate precautions to avoid direct eye or skin contact and the generation of aerosols or mists. Notify the monitor of any unintentional occupational exposure. A Material Safety Data Sheet (MSDS) describing the occupational hazards and recommended handling precautions will be provided to site staff if required by local laws or will otherwise be available from GSK upon request.

Investigational product must be stored in a secure area under the appropriate physical conditions for the product. Access to and administration of the investigational product will be limited to the investigator's authorized site staff. Mepolizumab must be stored under the appropriate physical conditions which includes storage in a refrigerator or at a temperature of 2-8°C and protected from light. Maintenance of a temperature log (manual or automated) is required. Investigational product must be dispensed or administered only to subjects enrolled in the study and in accordance with the protocol.

5.2. Dosage and Administration

Prior to administration, each vial of mepolizumab will need to be reconstituted and swirled gently to enable complete dissolution of the product. Detailed instructions can be found within the SPM.

Once the mepolizumab vial is reconstituted, 100 mg of mepolizumab should be drawn into a polypropylene syringe, and administered according to the instructions in the SPM.

Safety monitoring of subjects will occur during the SC administration and for one hour after the injection for the first 3 doses. After the first 3 doses, safety monitoring will be according to local site policy. Such monitoring will include general safety monitoring including monitoring for both systemic (ie, allergic/IgE-mediated and non-allergic) and local injection-site reactions. Trained rescue personnel and rescue medications/equipment must be available for use at all times. (See Section 6.3.1)

5.3. Treatment Assignment

All subjects will receive 100 mg of mepolizumab administered subcutaneously into the upper thigh or the upper arm approximately every 4 weeks.

5.4. Blinding

This study is open label.

5.5. Product Accountability

In accordance with local regulatory requirements, the investigator, designated site staff, or head of the medical institution (where applicable) must document the amount of investigational product dispensed and/or administered to study subjects and the amount received from and returned to GSK, when applicable. Product accountability records must be maintained throughout the course of the study.

5.6. Treatment Compliance

All doses administered within the study unit will be administered under the supervision of the Investigator, designee or study nurses.

Drug dispensing/accountability logs will be maintained by a member of the study team designated by the Investigator.

5.7. Concomitant Medications and Non-Drug Therapies

5.7.1. Permitted Medications and Non-Drug Therapies

All concomitant medications taken during the study will be recorded in the electronic case report form (eCRF). The minimum requirement is that drug name and the dates of administration are to be recorded. However, for corticosteroids, the dose must be recorded as well as any dose changes.

Additional medications to treat asthma are permitted, as are medications to treat other disease states, with the exception of those listed as prohibited. Oxygen and Continuous Positive Airway Pressure (CPAP) are permitted for the treatment of obstructive sleep apnea.

5.7.2. Prohibited Medications and Non-Drug Therapies

The following medications are not allowed prior to screening according to the following schedule or during the study:

Table 1 Medications not allowed prior to the screening visit and throughout the study

Medication	Washout Time Prior to Screening Visit
Investigational drugs	1 month or 5 half-lives whichever is longer
Omalizumab [Xolair]	130 days
Other monoclonal antibodies	5 half-lives
Experimental anti-inflammatory drugs (non biologicals)	3 months
Immunosuppressive medications such as those listed below (not all inclusive)	

 • Corticosteroids intramuscular, long-acting depot if used to treat a condition other than asthma 	3 months

 • Methotrexate, troleandomycin, cyclosporin, azathioprine 	1 month

 • Oral gold 	3 months

 • Chemotherapy used for conditions other than asthma 	12 months

 • Regular systemic (oral or parenteral) corticosteroids for the treatment of conditions other than asthma 	3 months

Additionally, Bronchial Thermoplasty and Radiotherapy are excluded for 12 months prior to Visit 1 and for the duration of the study. Neither CPAP nor oxygen therapy may be initiated after Visit 1.

5.8. Treatment after the End of the Study

The investigator is responsible for ensuring that consideration has been given to the post-study care of the subject's medical condition whether or not GSK is providing specific post study treatment. At the end of the study, subjects should be prescribed appropriate alternative asthma therapy if needed and as determined by the study Investigator.

5.9. Treatment of Study Treatment Overdose

The dose of mepolizumab considered to be an overdose has not been defined. There are no known antidotes and GSK does not recommend a specific treatment in the event of a suspected overdose. The investigator will use clinical judgement in treating the symptoms of a suspected overdose.

6. STUDY ASSESSMENTS AND PROCEDURES

Table 2 Time and Events Table for the First Year

Procedures	Screen	Baseline	Treatment (window is \pm 1 week)												Follow-up 4 weeks post last injection ⁶
	1	2	3	4	5	6	7	8	9	10	11	12	13	14	
Week of study	-4 to -1	0	4	8	12	16	20	24	28	32	36	40	44	48	
Written Informed Consent	X														
Medical History changes	X														
Assess cardiac risk factors	X														
Immunogenicity status	X														
Smoking status	X														
Prior monoclonal antibody use	X														
Parasite screening ³	X														
Exacerbations post completion of MEA 112997	X														
Inclusion/Exclusion Criteria	X	X													
Safety Assessments															
Concomitant Medication	X	X	X	X	X	X	X	X	X	X	X	X	X	X	
Physical Examination	X														X
Vital Signs	X	X	X	X	X	X	X	X	X	X	X	X	X	X	X
12-lead ECG	X							X						X	X
Adverse Events	X	X	X	X	X	X	X	X	X	X	X	X	X	X	X
Serious Adverse Events	X	X	X	X	X	X	X	X	X	X	X	X	X	X	X
Laboratory Assessments⁴															
Haematology	X		X		X			X			X			X	X
Chemistry plus lipoproteins ⁵		X												X	
Chemistry	X		X	X	X			X			X				X
Pregnancy Test ¹	S	U	U	U	U	U	U	U	U	U	U	U	U	U	U
Immunogenicity		X	X				*	X	*	*	*	*	*	X	X
HbsAg and hepatitis C antibody ²	X														
Efficacy Assessments															

Procedures	Screen	Baseline	Treatment (window is \pm 1 week)												Follow-up 4 weeks post last injection ⁶
	1	2	3	4	5	6	7	8	9	10	11	12	13	14	
Week of study	-4 to -1	0	4	8	12	16	20	24	28	32	36	40	44	48	
Exacerbation review		X	X	X	X	X	X	X	X	X	X	X	X	X	X
Asthma Control Questionnaire-5		X			X			X			X			X	X
Spirometry-		X			X			X						X	
Worksheets/IP/eCRF															
Administer Investigational Product.		X	X	X	X	X	X	X	X	X	X	X	X	X	X
Dispense paper worksheet	X	X	X	X	X	X	X	X	X	X	X	X	X	X	X
Collect paper worksheet		X	X	X	X	X	X	X	X	X	X	X	X	X	X
Phone IVRS	X	X	X	X	X	X	X	X	X	X	X	X	X	X	X
Complete eCRF	X	X	X	X	X	X	X	X	X	X	X	X	X	X	X

1. Pregnancy test (all females) U = Urine, S= Serum
 2. Hepatitis B Surface Antigen and Hepatitis C antibody (if Hepatitis C antibody positive, a hepatitis C confirmatory test should be automatically performed to confirm the result)
 3. Parasitic screening only in countries with a high-risk or for subjects who have visited high-risk countries in the past 6 months. Sites should utilise local laboratories.
 4. All laboratory assessments to be completed prior to dosing
 5. Subject must be in the fasting state. If subject has not fasted, may return the next business day to obtain this sample
 6. Follow-up visit window is \pm 1 week
- * Take additional immunogenicity sample immediately prior to first dose with 100mg vial and prior to the second dose with the 100mg vial. Maximum of 2 additional samples

Table 3 Time and Events Table for Additional Years

Procedures	Treatment subsequent years (repeat 48 week cycle for each subsequent year)													Follow-up 4 weeks post last injection ⁴
	15	16	17	18	19	20	21	22	23	24	25	26	27	
Week of study (± 1 week)	52	56	60	64	68	72	76	80	84	88	92	96	100	
Safety Assessments														
Assess Risk: Benefit ratio	X													
Concomitant Medication	X	X	X	X	X	X	X	X	X	X	X	X	X	
Physical Examination	X													X
Vital Signs	X	X	X	X	X	X	X	X	X	X	X	X	X	X
12-lead ECG						X						X		X
Adverse Events/SAEs	X	X	X	X	X	X	X	X	X	X	X	X	X	X
Laboratory Assessments²														
Haematology						X						X		X
Chemistry plus lipoproteins ³												X		
Chemistry						X								X
Pregnancy Test ¹	U	U	U	U	U	U	U	U	U	U	U	U	U	U
Immunogenicity	*	*	*	*	*	X	*	*	*	*	*	X		X
Efficacy Assessments														
Exacerbation review (worksheet)	X	X	X	X	X	X	X	X	X	X	X	X	X	X
Asthma Control Questionnaire			X			X			X			X		X
Spirometry-						X						X		
IP/eCRF/Worksheets														
Administer IP	X	X	X	X	X	X	X	X	X	X	X	X	X	
Dispense paper diary card	X	X	X	X	X	X	X	X	X	X	X	X	X	
Collect paper diary card	X	X	X	X	X	X	X	X	X	X	X	X	X	X
Phone IVRS	X	X	X	X	X	X	X	X	X	X	X	X	X	
Complete eCRF	X	X	X	X	X	X	X	X	X	X	X	X	X	X

1. Pregnancy test (all females) U = Urine

2. All laboratory tests are to be completed prior to dosing

3. Subject must be in the fasting state. If subject has not fasted, may return the next business day to obtain this sample

4. Follow-up visit window is ± 1 weeks

* Take additional immunogenicity sample immediately prior to first dose with 100mg vial and prior to the second dose with the 100mg vial. Maximum of 2 additional samples

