- The risk/benefit profile for the subject is no longer positive in the opinion of the investigator **or**
- the subject's physician withdraws the subject **or**
- the subject withdraws consent **or**
- the sponsor discontinues development of mepolizumab **or**
- the sponsor discontinues the study in the relevant participating country **or**
- mepolizumab becomes commercially available in the relevant participating country

Subjects will remain on standard of care asthma therapy, which may be adjusted during the study, at the discretion of their physician. The use of Xolair (omalizumab) or any other monoclonal antibody will not be permitted during the course of the study.

Subjects will be monitored in the clinic approximately every 4 weeks to assess adverse events and asthma status. The Asthma Control Questionnaire-5 (ACQ) will be used to assist the investigator in assessing the subject's asthma status along with spirometry at regular intervals. As some subjects may have previously received placebo while participating in the MEA112997 study and are naive to mepolizumab, safety lab monitoring will be more frequent at the start of the study. Appropriate safety labs will be drawn prior to starting treatment and then at week 4, 8, 12, 24, 36 and 48. Thereafter, these will be collected every 24 weeks. Labs will also be obtained at 4 weeks after discontinuing mepolizumab. Subjects discontinuing mepolizumab treatment should be monitored for exacerbation of their asthma.

Serum samples for anti-mepolizumab antibody measurements will be obtained from all subjects at Weeks 0, 4, 24 and 48 of the initial year, week 24 and 48 for every additional year, as well as at the Follow-up Visit. Any anti-mepolizumab antibody positive sample will be tested for neutralization antibody.

A maximum of two additional anti-mepolizumab antibody samples will be obtained; one immediately prior to the first dose and the other prior to the second dose with the 100mg mepolizumab vial. If the first or second dose coincides with a visit where an immunogenicity sample is already required, it is not necessary to obtain an additional sample.

The number of subjects participating in this trial will be no greater than the number of subjects randomised into MEA112997 who also received 2 doses of study medication which is 608 subjects.

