4.2. Inclusion Criteria

Specific information regarding warnings, precautions, contraindications, adverse events, and other pertinent information on the GSK investigational product or other study treatment that may impact subject eligibility is provided [GlaxoSmithKline Document Number [CM2003/00010/07](#)].

Deviations from inclusion criteria are not allowed because they can potentially jeopardise the scientific integrity of the study, regulatory acceptability or subject safety. Therefore, adherence to the criteria as specified in the protocol is essential.

Subjects eligible for enrolment in the study must meet all of the following criteria:

1. **Informed Consent:** Prior to commencing any study related activities, subjects must be able and willing to provide written informed consent.
2. **MEA112997 Study Participation:** Received at least 2 doses of double-blind investigational product during the MEA112997 trial.
3. **MEA112997 Treatment Assignment:** If the subject received mepolizumab, they must have had a positive risk: benefit ratio in the opinion of the investigator.
4. **Current Anti-Asthma Therapy:** Asthma is currently being treated with a controller medication and the subject has been on a controller medication for the past 12 weeks. Subjects will be expected to continue controller therapy for the duration of the study.
5. **Male or Eligible Female Subjects:**

To be eligible for entry into the study, **females of childbearing potential** must commit to consistent and correct use of an acceptable method of birth control ([Appendix 2](#)) for the duration of the trial and for 4 months after the last study drug administration.

A serum pregnancy test is required of **all** females. at the initial Screening Visit (Visit 1). In addition, a urine pregnancy test will be performed for **all** females prior to Visit 2, during each scheduled study visit prior to the injection of investigational product, and during the Follow-up Visit.

French subjects: In France, a subject will be eligible for inclusion in this study only if either affiliated to or a beneficiary of a social security category.

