4.5. Withdrawal Criteria

Subjects may be withdrawn from study treatment at anytime by the Investigator if it is considered to be detrimental for them to continue in the study. Reasons for withdrawal can include: an adverse event, lost to follow-up, protocol violation, lack of efficacy, sponsor terminated study, non-compliance, pregnancy, abnormal liver function test, abnormal laboratory results, or for any other reason. Liver chemistry stopping criteria are detailed in Section 6.3.2. In addition, QTc discontinuation criteria are listed below:

- QTc(F)>500 msec or uncorrected QT>600 msec
- Bundle branch block: QTc(F)>530 msec (**Note:** QTc(F)>500 msec for Korean subjects)
- Change from baseline: QTc > 60msec

[Based on average QTc(F) value of triplicate ECGs. If an ECG demonstrates a prolonged QT interval, obtain 2 more ECGs over a brief period, and then use the averaged QTc(F) values of the 3 ECGs to determine whether the patients should be discontinued from the study].

Subjects are free to discontinue participation in the study at anytime. Every effort should be made to have the subject return for a Follow-up visit 4 weeks post last mepolizumab injection. In those instances where the subject specifies the reason for withdrawal of consent, this information will be captured in the eCRF.

A subject should only be designated as lost to follow-up if the site is unable to establish contact with the subject after 3 documented attempts via 2 different methods (phone, text, e-mail, certified letter, etc). These efforts should be documented in the clinic notes at the site.

Subjects may also be withdrawn from this study if mepolizumab becomes commercially available in the respective country, marketing of mepolizumab is no longer being sought in the respective country, or upon decision of the sponsor to discontinue further development of mepolizumab.

The primary reason for withdrawal will be recorded in the eCRF and any data collected up until the point of withdrawal will be used in the data analyses.

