6.3.8. Time Period and Frequency of Detecting AEs and SAEs

The investigator or site staff is responsible for detecting, documenting and reporting events that meet the definition of an AE or SAE.

AEs will be collected from the start of investigational product (Visit 2) and until the follow up visit (4 weeks after the last injection).

SAEs will be collected over the same time period as stated above for AEs. However, any SAEs assessed **as related** to study participation (e.g., study treatment, protocol-mandated procedures, invasive tests, or change in existing therapy) or related to a GSK concomitant medication, will be recorded from the time a subject consents to participate in the study up to and including any follow up contact. All SAEs will be reported to GSK within 24 hours, as indicated in Section [6.3.9](#).

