6.4. Immunogenicity

Blood samples will be collected for the determination of anti-mepolizumab antibodies, just prior to administration of mepolizumab, at the time points identified in the Time and Events Table (see [Table 2](#) and [Table 3](#)). Samples that test positive for anti-mepolizumab antibodies will be further tested for the presence of neutralising antibody.

A maximum of two additional anti-mepolizumab antibody samples will be obtained; one immediately prior to the first dose and the other prior to the second dose with the 100mg mepolizumab vial. If the first or second dose coincides with a visit where an immunogenicity sample is already required, it is not necessary to obtain an additional sample.

For all subjects, immunogenicity testing will occur at 4 weeks after the last dose.

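### Protocol Table 2 marks a mepolizumab dose at the Follow-up visit, which the same table defines as falling 4 weeks after the last injection

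*Protocol*

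**What the plan says.** Table 2 in Protocol Section 6 has columns for Visits 1 to 14 and a final column headed "Follow-up 4 weeks post last injection". Its row "Administer Investigational Product" is blank at Visit 1 (Screen), marked at Visits 2 to 14, and marked again in that final column.

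The rest of the protocol describes Follow-up differently:

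- **Table 3** (later years): the row "Administer IP" is marked at Visits 15 to 27 and blank at Follow-up.
- **Section 4.5**: subjects who stop should return for a "Follow-up visit 4 weeks post last mepolizumab injection".
- **Section 6.3.8**: adverse events are collected "until the follow up visit (4 weeks after the last injection").
- **Section 6.4**: for all subjects, "immunogenicity testing will occur at 4 weeks after the last dose".
- **Protocol Summary, Study Design**: "Labs will also be obtained at 4 weeks after discontinuing mepolizumab".
- **Section 4.2, criterion 5**: urine pregnancy tests take place "during each scheduled study visit prior to the injection of investigational product, and during the Follow-up Visit", which lists Follow-up apart from the visits with an injection.

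Footnote 6 to Table 2 gives the Follow-up window as ±1 week and does not mention dosing. Section 3.1 states that sites must adhere to the Time and Events Table.

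**The concern.** Read literally, the schedule tells the site to inject at the exit visit, while the header of the same column says the last injection was 4 weeks earlier. Both cannot be true.

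Sites work from this table visit by visit, and Section 3.1 allows waivers only for immediate safety concerns. The interval between doses and the interval from last injection to Follow-up are both 4 weeks, so a dose at Follow-up would not look out of place by its timing. Follow-up is also where adverse event collection ends, and Table 2 schedules nothing after it. A dose given there would, under Sections 4.5, 6.3.8 and 6.4, call for a further visit 4 weeks later that the table does not provide.

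The column also serves subjects who stopped for safety reasons. Section 6.3.2 forbids re-challenge after a liver stopping criterion is met, and the mark carries no exception for them.

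**Working it through.** There is no sample size, power or error-rate figure to reproduce. The check is a count of cells, a comparison of the two tables, and a comparison of timings.

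**1. Dosing visits in year 1.** From Table 2, doses fall at Weeks 0, 4, ..., 48. Number of visits = 48/4 + 1 = 13 (Visits 2 to 14).

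**2. Marks in the Table 2 dosing row.** The row has a label and 15 cells (14 visits plus Follow-up), matching the header. Screen is blank and the other 14 cells are X. Surplus = 14 − 13 = 1, located in the Follow-up cell.

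**3. The same count in Table 3.** The row has a label and 14 cells (Visits 15 to 27 plus Follow-up), with 13 X for 13 visits. Surplus = 13 − 13 = 0, and Follow-up is blank.

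**4. Could the columns have shifted when the table was read?** Other Table 2 rows serve as controls:

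| Row | X marks | Follow-up cell |
|---|---|---|
| Concomitant Medication | 14 | blank |
| Vital Signs | 15 | X |
| Spirometry | 4 | blank |
| Dosing row | 14 | X |

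Each row has the same number of cells as the header, and the dosing row's Screen cell is correctly blank. A shift by one column would have disturbed one or the other. Spirometry is in the same table fragment as the dosing row and keeps its blank, so blank Follow-up cells survive there.

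**5. The block around the dosing row.** All five rows of the worksheets/IP/eCRF block end in X in Table 2. Compared with Table 3 at Follow-up:

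| Row | Table 2 | Table 3 |
|---|---|---|
| Administer product | X | blank |
| Dispense worksheet or diary card | X | blank |
| Collect worksheet or diary card | X | X |
| Phone IVRS | X | blank |
| Complete eCRF | X | X |

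Three of the five rows differ. This fits marks being carried across the block when the table was drafted. It would also fit a reading fault confined to that block.

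**6. Timing.** Section 5.3 sets dosing at about every 4 weeks, and Table 2 allows ±1 week. If the previous dose was on schedule, the next is due at day 28 ± 7. Follow-up is at day 28 ± 7 after the last injection, which is days 21 to 35. The two windows coincide.

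**7. Is a dose at Follow-up permitted anywhere?** No section or footnote provides for one. The amendment history in Appendix 7 records changes to the Follow-up column header and window, but none that adds a dose at that visit.

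**The case against.** The strongest objection concerns the evidence. It is one machine-read cell, and the control rows lie outside the block in question. They show that blanks survive elsewhere, including in the same fragment, but not that this block was read correctly. A matching cell count argues against a shifted column without excluding a wrongly filled last cell. This stands as a reason to look at the printed table before acting. It does not outweigh the reading, because the cell count, the blank Screen cell and the Spirometry row all agree with it.

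The second objection is that the mark corrects itself. The column header rules out an injection. Section 3.1 continues dosing only until a listed stopping event, and Section 6.3.2 requires immediate withdrawal of product and no re-challenge after a liver stopping criterion. A careful site would not dose. This also stands, and it is why the risk is small. It does not make the mark correct: a binding schedule should not have to be overridden by its own column header.

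Third, the conflicting sections are not independent evidence. Sections 4.5, 6.3.8 and 6.4 and the Summary restate one fact, that Follow-up comes 4 weeks after the last dose, and criterion 5 is about pregnancy tests. That is fair. There is one mismatch, and the several references show only that the rest of the protocol agrees on which side is right.

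**Conclusion.** The concern holds as a minor inconsistency. As the table reads, Table 2 has one surplus dosing mark, 14 against 13 dosing visits, and it instructs a dose at a visit defined by the absence of one.

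The exposure is at most one unintended 100 mg dose per subject leaving in year 1. The documents do not say how many subjects leave then. Enrolment is capped at 608, which is a ceiling and not an estimate of the number affected. The intended schedule, no dose at Follow-up, can be inferred from the header and the other sections, so the practical risk is small. No endpoint, analysis population or estimate in the plan is wrong because of it.

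Confidence is medium. The conclusion assumes that the printed Table 2 carries the X in that cell. If it does not, the concern falls away.

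**What to change.** Check the printed Table 2. If the mark is there, delete the Follow-up X from the dosing row. The row then has 13 marks at Visits 2 to 14 and a blank Follow-up cell, the same pattern as Table 3. Tell sites by administrative letter or at the next amendment. The column header, Table 3 and Sections 4.5, 6.3.8 and 6.4 need no change.

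The worksheet-dispensing and Phone IVRS rows also differ between the two tables at Follow-up and could be reconciled at the same time. The documents do not show which table is right for those rows, so the sponsor would have to decide.

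The cost is one deleted mark and one notice to sites. No analysis changes.
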